6.5. Assessment of Tumor Response

The procedures to assess tumor response will be conducted every 8 weeks during the first 24 weeks on study and then every 12 weeks up to 72 weeks, regardless of cycle number and regardless of any dose interruptions (ie, Weeks 8, 16, 24, 36, 48, 60, 72, etc). Tumor assessments must be done any time during the specified week (+/-3 days around the week). Therefore there is a 13-day window to conduct tumor assessments that begins 3 days prior to the start of the last week of the corresponding 28-day cycle and ends 3 days after the last day of that same corresponding cycle. The description of the assessments to be conducted are detailed in Section [6.12](#) and outlined in the Study Procedures Table in [Appendix 2](#).

A bone marrow biopsy and aspirate will be collected for all subjects who achieve a CR for confirmatory purpose. For LPL/WM without adenopathy and CLL subjects a bone marrow biopsy/aspirate will be collected to confirm a PD if based only upon declines in the platelet count and/or hemoglobin for CLL subjects or rise in Serum monoclonal IgM in LPL/WM. For all LPL/WM patients who achieve CR or PD and are not evaluable by radiological criteria require confirmation by bone marrow evaluation. If the subject does not otherwise meet criteria for CR or if the nature of PD does not require bone marrow confirmations, it is not necessary to obtain a bone marrow biopsy/aspirate (See Sections [6.20](#) and [6.21](#)).

ONLY for subjects with LPL/WM, an evaluation of serum monoclonal IgM by both SPEP and IFE will be conducted including cryoglobulin testing (LPL/WM enrollment limited to those sites which have cryoglobulin analysis capabilities). Serum monoclonal IgM as assessed by SPEP will only be considered if baseline total serum IgM quantitation by nephelometry is not available.

This procedure should be conducted on the Day 1 visit occurring during the week window allotted for tumor response assessments. LPL/WM subjects who do not have lymphadenopathy on their screening CT/MRI evaluations are not required to have repeated scans for tumor assessment unless clinically indicated, but all subjects in this subset will require BM evaluations for suspected PD or CR assessments.

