Subjects who stop study drug for reasons other than progression of disease (eg, experience unacceptable toxicity) should be continued on the study and followed every 6 months or according to institutional standard of care (if more frequent) until progression is documented or another anti-tumor regimen is initiated. An end of study visit need only to be conducted per Section [6.7](#) if the subject comes off of study and is no longer to be followed.

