6.5.1. Clinical Evaluation after 72 weeks (18 months)

After 72 weeks on study, the subject will be followed for disease status at a minimum of every 6 months or according to institutional standard of care (if more frequent). At each study visit the subject's disease status will be assessed and information will be collected to determine response to treatment. If no change in disease status is identified and the subject is dispensed additional GS-9973/GS-9973 SDD, the most recent prior response documented for the study will be recorded.

All subjects with CLL should have the following laboratory test results recorded at each visit: ALC, PLT, Hgb, ANC. All subjects with WM should have the following laboratory test results recorded at each evaluation visit: IgM, serum M protein.

All subjects will have a CT scan at least once every 6 months and at time of clinical change in response (PR or CR after SD, or CR after PR) or progression. In addition, for initial CR a bone marrow evaluation is required.

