6.6. At Disease Progression

All subjects will be followed until initiation of next treatment. If the subject was not receiving study drug at the time tumor progression was documented, or was at a dose level below the maximum and could potentially tolerate a higher dose, after discussion with the Gilead Sciences Medical Monitor, the subject may continue on study and study drug may be re-started or escalated using the algorithm defined in Section [5.3.5](#) if the investigator feels it is in the subject's best interests to do so.

If the investigator feels the subject is having progressive disease, tumor imaging as described in Section 6.12 should be carried out unless the most recent imaging had documented progressive disease. The images and any other material needed to document progression are to be transferred to the IRC as soon as possible. While waiting for confirmation of progressive disease from the IRC, the subject should continue to receive study drug unless his/her medical condition warrants immediate treatment with different therapy. When progression is confirmed, the following procedures should be carried out while the subject is still receiving study drug.

- Complete physical examination including weight
- Vital signs including blood pressure, respiratory rate, pulse, oxygen saturation by pulse oximetry, temperature
- Karnofsky performance status (see Section 6.9.3)
- Concomitant Medication Review
- Obtain blood samples for:
 - Chemistry (see Section 6.9.8)
 - Hematology (see Section 6.9.8)
 - Coagulation (see Section 6.9.8)
 - GS-9973/GS-9973 SDD plasma concentration (excluding subjects off study drug at time of progression)

For subjects with SLL, CLL or MCL

- CTC Molecular characterization (see Section 6.14)
- Cytokines and chemokines (see Section 6.13.1)
- CTC RNA pre-dose (see Section 6.13.2)

CCI

- Record the approximate number of hours between the last 2 doses of study drug and the time the blood samples for plasma concentration were obtained (excluding subjects off study drug at time of progression)
- Urine pregnancy test (females of childbearing potential)

- For CLL subjects a bone marrow biopsy/aspirate will be collected to confirm a PD. If the nature of PD does not require bone marrow confirmations, it is not necessary to obtain a bone marrow biopsy/aspirate (See Section [6.20](#)).
- Collect used/unused study drug and assess study drug compliance by pill counts (excluding subjects off study drug at time of progression)

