6.7. End of Study

The following procedures will be conducted when a subject goes off study and prior to initiating a new anti-tumor regimen. If a subject stops study drug for a reason other than progressive disease, they will be followed as per the scheduled imaging in Section [6.5](#) with additional CBC (hematology) at time of assessments. If the subject chooses not to continue participation on the study once study drug has been stopped or it is not consistent with good medical practice then the end of study procedures listed below are to be conducted within 30 days of the last dose of study drug or prior to initiating a new anti-tumor regimen. Please see Study Procedures Table in [Appendix 2](#).

The end of study visit and disease progression visit Section [6.6](#) can occur simultaneously; however, if the end of study visit was not performed at the same time as disease progression, perform the following:

- Complete physical examination including weight
- Vital signs including blood pressure, respiratory rate, pulse, oxygen saturation by pulse oximetry, temperature
- Karnofsky performance status (see Section [6.9.3](#))
- Concomitant Medication Review
- Obtain blood samples for:
 - Chemistry (see Section [6.9.8](#))
 - Hematology (see Section [6.9.8](#))
 - Coagulation (see Section [6.9.8](#))
 - GS-9973/GS-9973 SDD plasma concentration

For subjects with SLL, CLL or MCL

- CTC Molecular characterization (see Section [6.14](#))
- Cytokines and chemokines(see Section [6.13.1](#))
- CTC RNA pre-dose (see Section [6.13.2](#))
- Record the approximate number of hours between the last 2 doses of GS-9973/GS-9973 SDD and the time the blood samples for plasma concentration were obtained
- Urine pregnancy test (females of childbearing potential)
- Collect used/unused study drug and assess study drug compliance by pill counts
- Tumor response assessment (according to Section [6.5](#)), if not conducted within the last 4 weeks
- Record any AEs
- Complete subject/visit information in IxRS

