6.12. Tumor Imaging (CT or MRI)

CT or MRI scans will be obtained to document sites of disease, identify target lesions as described in Section 6.20.4 and 6.21.4 and to assess response and disease progression. CT scan is the preferred method for radiographic tumor assessment. MRI scanning may be used at the investigator's discretion in subjects for whom this may be a preferred alternative to CT scanning; however, if MRI is performed, a non-contrast CT of the chest should also be performed. Contrast-enhanced scanning is preferred, but iodine-containing or gadolinium contrast material may be omitted in subjects for whom use of a contrast agent would be medically contraindicated. Imaging of the neck, chest, abdomen and pelvis by CT scan (with contrast) or MRI will be performed as part of the Screening Procedures (or within 5 weeks before Dosing Day 1 if the scan was performed as part of standard medical practice). Imaging will then occur every 8 weeks from Cycle 1 Day 1 date during the first 24 weeks of the study and then every 12 weeks thereafter until week 72 regardless of any dose interruptions. After week 72 scans will occur at least every 6 months (\pm 4 weeks). At all timepoints after Screening, imaging of the chest, abdomen, and pelvis will be required. Imaging of the neck is required at each follow-up time point if the neck scan was positive at baseline or if palpable neck lymphadenopathy appears during the course of the study.

The imaging procedure and specification (eg, the same contrast agent, slice thickness, etc.) used to define measurable target and non-target lesions must be used throughout the study for each subject. Any subject with symptoms suggestive of disease progression should be evaluated for tumor response at the time the symptoms occur. Tumor burden will be characterized at baseline and subsequent response assessments will be carried out according to Section 3. Scans need to be of high quality and digitalized in the Digital Imaging and Communication in Medicine (DICOM) format to be collected and to allow for reading by the IRC (see Section 9.4).

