6.20.3. Timing of Assessments

During screening, clinical and imaging-based tumor assessments should be performed within 5 weeks prior to the start of study drug. Clinical tumor assessments should be performed at each clinic visit. On-study CT/MRI tumor assessments should be performed at ~8- to 12-week intervals. An End of Study CT/MRI tumor assessment should be performed unless the subject already has radiographic confirmation of disease progression \leq 4 weeks prior to study discontinuation. If a subject permanently discontinues study drug prior to objective documentation of NHL progression, investigators should continue further follow-up at ~8 or ~12-week intervals until NHL progression is documented.

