6.21.3. Timing of Assessments

During screening, clinical and imaging-based tumor assessments should be performed within 5 weeks prior to the start of study drug. Clinical tumor assessments should be performed at each clinic visit. On-study CT/MRI tumor assessments should be performed at ~8- to 12-week intervals. An End of Study CT/MRI tumor assessment should be performed unless the subject already has radiographic confirmation of disease progression \leq 4 weeks prior to study drug discontinuation. If a subject permanently discontinues study drug prior to objective documentation of CLL progression, investigators should continue further follow-up at ~8 or ~12-week intervals until CLL progression is documented.

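### Protocol Section 6.5 gives subjects who stop drug without progression a 6-month follow-up interval that conflicts with the 8/12-week assessments stated elsewhere, and at its minimum could censor a progression before Week 16 or 24 out of the primary Kaplan-Meier rate

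*Protocol*

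**What the plan says.** Protocol Section 6.5 sets tumor assessments "conducted every 8 weeks during the first 24 weeks on study and then every 12 weeks up to 72 weeks, regardless of cycle number" and irrespective of dose interruptions, which gives Weeks 8, 16, 24, 36, 48, 60 and 72. Later in the same section, subjects who stop drug for a reason other than progression "should be continued on the study and followed every 6 months or according to institutional standard of care (if more frequent) until progression". A new anti-tumor treatment also ends this follow-up. That sentence has no Week 72 limit. Similar 6-month wording appears in Section 6.5.1, where it is limited in time: "After 72 weeks on study, the subject will be followed for disease status at a minimum of every 6 months".

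Other current text gives off-drug subjects a shorter interval:

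- Section 6.20.3 (NHL), after permanent discontinuation without progression: "investigators should continue further follow-up at ~8 or ~12-week intervals until NHL progression is documented".
- Section 6.21.3 (CLL), same situation: "investigators should continue further follow-up at ~8 or ~12-week intervals until CLL progression is documented".
- Footnote i of Protocol Appendix 2 and footnote i of SAP Appendix 1 say the same.
- Section 6.7 says of subjects who stop for a reason other than progression that "they will be followed as per the scheduled imaging in Section" 6.5. Footnote c in both schedules repeats this.
- Section 6.12 runs imaging from Cycle 1 Day 1 at 8- and then 12-week intervals to Week 72.

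The primary endpoint is the Kaplan-Meier (KM) progression-free rate by independent review at Week 16 or Week 24, depending on cohort (Protocol 8.5.2.1, SAP 6.1.2). Progression or death after two or more consecutive missing assessments is censored at the last adequate assessment, or at Study Day 1 if there is none (Protocol 8.4.2; SAP 6.1.1 and Table 13-1). SAP Appendix 2 dates progression at the time point when it is first identified.

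**The concern.** Section 6.5's 6-month sentence and the 8/12-week text cannot both be the minimum for the same subjects. The 6-month sentence is the only one in Section 6.5 written specifically for subjects who have stopped drug, so a site that follows it is complying with the protocol. The same paragraph requires the end-of-study visit, which carries a tumor assessment, only if the subject leaves the study. No scan near the landmark is therefore required of these subjects under that sentence.

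At stake is how progression is ascertained for the primary endpoint. A progression that occurs before Week 16 or 24 but is first seen at the 6-month visit would be handled by the missed-assessment rule and would not enter the KM rate as a failure.

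**Working it through.** **Yardstick from the plan.** No figure in the documents depends on the off-drug interval, so I use Protocol Table 8-1 for scale. With 8 of 40 responders the posterior is Beta(8.5, 33.5). Its mean is 8.5/42 = 0.202 and its 95% interval is 0.097 to 0.335, which reproduces the table. The half-width is (33.5 - 9.7)/2 = 11.9 points.

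**Step 1: assessments skipped.** Section 6.5.1 equates 72 weeks with 18 months, so 6 months = 24 weeks. Counting from the last scan:

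| Last scan | Next visit | Scheduled assessments skipped |
|---|---|---|
| None (Day 1) | Week 24 | 8, 16 |
| Week 8 | Week 32 | 16, 24 |
| Week 16 | Week 40 | 24, 36 |

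Counting from the stop date instead, for every quarter-week stop time before Week 24 and with 6 months taken as 24 or 26 weeks, the number skipped is never below 2.

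**Step 2: apply the rule.** Against the 8/12-week calendar, a progression found at that visit follows at least two consecutive missing assessments. It is censored at the last adequate scan or Day 1.

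**Step 3: size.** The documents give no stopping share or off-drug hazard, so these are assumptions:

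- A share p (0.05, 0.10 or 0.20) stops progression-free at week s: 4 or 12, and also 20 where the landmark is Week 24.
- On-drug hazard is λ and off-drug hazard is hλ, with h = 1, 1.5 or 2.
- The landmark is L = 16 or 24. The next visit is V = s + 24, with no earlier scan.

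Formulas:

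- on = (exp(-λs) - p) × exp(-λ(L - s))
- true rate = on + p × exp(-hλ(L - s)), solved for λ
- w = p × exp(-hλ(V - s)), the stoppers still progression-free at V
- S0 = exp(-λ × week of last scan)
- KM rate = S0 × (on + w) / (S0 - (p - w))

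*Low end, true 20%, p = 0.10 (L = 16, s = 12, h = 1).* λ = 0.1006; on = (0.2991 - 0.10) × 0.6687 = 0.1331; w = 0.0089; S0 = 0.4472. KM = 0.4472 × 0.1421/0.3562 = 17.8%, or -2.2 points. These subjects are known to be progression-free at the stop, but censoring them back at Week 8 discards that time.

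*High end, true 20%, p = 0.10 (L = 24, s = 4, h = 2).* λ = 0.0630; on = (0.7772 - 0.10) × 0.2835 = 0.1920; w = 0.0049; S0 = 1. KM = 0.1968/0.9049 = 21.8%, or +1.8 points. Here stoppers progress faster than those who stay on, and are removed from the risk set.

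Over the full grid:

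| True rate | Stopping share | Shift in KM rate (points) |
|---|---|---|
| 20% | 5% | -1.0 to +0.8 |
| 20% | 10% | -2.2 to +1.8 |
| 20% | 20% | -5.8 to +3.8 |
| 50% | 10% | -0.3 to +3.2 |

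One grid point (L = 16, s = 4, h = 2, p = 0.10, true 20%) gives 21.2% by formula and 21.1% in a simulation of 400,000 subjects.

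**Hand check.** Take N = 40. Eight on-drug subjects are progression-free at the landmark. Four stop before any scan and all four are first shown to have progressed at the 6-month visit. They are censored at Day 1, so KM = 8/36 = 22.2%. If all four progressed by the landmark, the truth is 8/40 = 20.0%. If two did, it is 10/40 = 25.0%. The sign depends on when they progressed.

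**The case against.** The strongest reply is that the documents lean to one calendar. The 6-month sentence names no imaging and keeps the subject on study, while Section 6.5 itself, Sections 6.7, 6.12, 6.20.3 and 6.21.3, and both schedules of assessments point to Weeks 8, 16, 24 and 36. This largely stands. A reader might infer that nothing in the plan says which calendar applies after drug is stopped. That goes too far: SAP Appendix 1 contains only one schedule before Week 72, and its footnotes c and i apply it to subjects off drug. The contradictory sentence nevertheless remains, and sites can act on it.

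A reader might also take the 6-month interval as the schedule against which assessments count as missing. Progressions would then be dated after the landmark and the rate would be inflated. SAP Appendix 1 does not support that reading, so no figure is given for it.

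Other scans limit the effect. Section 6.5 allows more frequent local practice. Section 6.12 says: "Any subject with symptoms suggestive of disease progression should be evaluated for tumor response at the time the symptoms occur". Section 6.6 says: "If the investigator feels the subject is having progressive disease, tumor imaging as described in Section 6.12 should be carried out". This stands, and is why the consequence is conditional.

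The extreme figures also need heavy stopping. The -2.2 case requires 0.10/0.299 = 33% of those still progression-free at Week 12 to stop at that moment, and the -5.8 case requires 67%. The model omits new anti-cancer therapy, which leads to censoring under either schedule. Both criticisms stand.

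**Conclusion.** The contradiction is real, is in current text and should be fixed. Its effect on the primary estimate is probably small and of uncertain sign: about -2 to +2 points at a true rate of 20% with 10% stopping early, less than one-fifth of the 11.9-point half-width at N = 40. That rests on assumed stopping shares and hazards, on sites using the 6-month minimum, and on no earlier scan. Confidence is high for the textual conflict and low for any particular numerical effect.

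Two further inferences are not supported. One is that uncounted progressions must inflate the rate; Step 3 and the hand check show both signs. The other is that the futility decisions are affected; Protocol Section 8.6 uses its own binary response rule, not this KM estimate.

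The imaging charter and the SAP derivation diagram were not available and might settle part of this.

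**What to change.** Reconcile the 6-month sentence in Protocol Section 6.5 with the rest of that section and with Sections 6.7, 6.12, 6.20.3, 6.21.3 and Appendix 2 footnotes b, c and i, so that one off-drug tumor-assessment schedule is stated. Check that it includes each cohort's Week 16 or 24 landmark. If Section 6.5.1 shows the intent, the 6-month interval would be confined to the period after Week 72; the sponsor should confirm this.

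Optionally, add a sentence to SAP Appendix 2 saying that scheduled and missing assessments refer to the SAP Appendix 1 calendar after drug stop as well. This is mainly a drafting clarification.

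The cost is one protocol clarification and, if wanted, one SAP sentence, with no new analysis and no change to the censoring rules. Off-drug subjects would have more scans than the 6-month sentence alone requires. Scans already missed in the cohorts that received the MM formulation, which are closed to enrollment (Protocol Table 5-1), cannot be recovered.

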6.5.1. Clinical Evaluation after 72 weeks (18 months)

After 72 weeks on study, the subject will be followed for disease status at a minimum of every 6 months or according to institutional standard of care (if more frequent). At each study visit the subject's disease status will be assessed and information will be collected to determine response to treatment. If no change in disease status is identified and the subject is dispensed additional GS-9973/GS-9973 SDD, the most recent prior response documented for the study will be recorded.

All subjects with CLL should have the following laboratory test results recorded at each visit: ALC, PLT, Hgb, ANC. All subjects with WM should have the following laboratory test results recorded at each evaluation visit: IgM, serum M protein.

All subjects will have a CT scan at least once every 6 months and at time of clinical change in response (PR or CR after SD, or CR after PR) or progression. In addition, for initial CR a bone marrow evaluation is required.

6.6. At Disease Progression

All subjects will be followed until initiation of next treatment. If the subject was not receiving study drug at the time tumor progression was documented, or was at a dose level below the maximum and could potentially tolerate a higher dose, after discussion with the Gilead Sciences Medical Monitor, the subject may continue on study and study drug may be re-started or escalated using the algorithm defined in Section [5.3.5](#) if the investigator feels it is in the subject's best interests to do so.

If the investigator feels the subject is having progressive disease, tumor imaging as described in Section 6.12 should be carried out unless the most recent imaging had documented progressive disease. The images and any other material needed to document progression are to be transferred to the IRC as soon as possible. While waiting for confirmation of progressive disease from the IRC, the subject should continue to receive study drug unless his/her medical condition warrants immediate treatment with different therapy. When progression is confirmed, the following procedures should be carried out while the subject is still receiving study drug.

- Complete physical examination including weight
- Vital signs including blood pressure, respiratory rate, pulse, oxygen saturation by pulse oximetry, temperature
- Karnofsky performance status (see Section 6.9.3)
- Concomitant Medication Review
- Obtain blood samples for:
 - Chemistry (see Section 6.9.8)
 - Hematology (see Section 6.9.8)
 - Coagulation (see Section 6.9.8)
 - GS-9973/GS-9973 SDD plasma concentration (excluding subjects off study drug at time of progression)

For subjects with SLL, CLL or MCL

- CTC Molecular characterization (see Section 6.14)
- Cytokines and chemokines (see Section 6.13.1)
- CTC RNA pre-dose (see Section 6.13.2)

CCI

- Record the approximate number of hours between the last 2 doses of study drug and the time the blood samples for plasma concentration were obtained (excluding subjects off study drug at time of progression)
- Urine pregnancy test (females of childbearing potential)

- For CLL subjects a bone marrow biopsy/aspirate will be collected to confirm a PD. If the nature of PD does not require bone marrow confirmations, it is not necessary to obtain a bone marrow biopsy/aspirate (See Section [6.20](#)).
- Collect used/unused study drug and assess study drug compliance by pill counts (excluding subjects off study drug at time of progression)
- Record any AEs
- Complete subject/visit information in IxRS

